**Social/Behavioral  
SECTION I**

**Therapeutic/Non-Therapeutic**

**Does your research involve a drug, medical device, technique or other intervention or strategy (including means like diet, cognitive therapy, behavioral therapy, exercise) to diagnose, treat or prevent a particular condition or disease: "THERAPEUTIC RESEARCH"?**

Yes

**1. Title of Protocol:**

Using Mobile Technology to Address the Trauma Mental Health Treatment Gap: Developing Implementation Protocols for Primary Care

**G. Are you a student or house officer?**

No

**3. Funding Source:**

**Check all that apply and provide the source of the funding.**

Cooperative Group:

Center for Clinical and Translational Research (CCTR)

Federal (e.g., NIH) Grant - Provide source:

♦ Other Grant: IDEA CTR-Pilot Team Building

Departmental funding

Commercial - Provide company name:

Department of Defense

Other - Provide source (e.g. personal funding):

**4. Deadline for IRB Approval:**

♦ Yes - Explain and provide date: ASAP. IDEA CTR would like final approval to be

submitted within 60 days from February 12th 2021

No

**5. Contract:**

**Is there a contract associated with this study?**

No

**6. Agreements**

**Is there a Material Transfer Agreement (MTA) associated with this study?**

No

**Is there a Data Use Agreement (DUA) associated with this study?**

No

**Is there a Data Transfer Agreement (DTA) associated with this study?**

No

**B. Will the research be conducted at external sites under the oversight of an external IRB?**

No

**C. Does UNMC, TNMC, CHMC or UNO serve as the lead site with responsibility for data and/or safety monitoring?**

Yes

**E. Does this study involve face to face contact with subjects?**

Yes

**Do you have any additional comments that you wish the IRB to consider during the review of this application?**

No

## **SECTION II**

### **PROTOCOL ABSTRACT**

**1. Provide a brief (less than 2500 characters) abstract of the research protocol.  
(2500 characters)**

**This summary should include: 1)) a brief description of the purpose of the study, 2) eligibility criteria, 3) interventions and evaluations and 4) follow-up.**

BounceBack Now (BBN) is a self-help, trauma-focused mental health mobile app with automated assessment with treatment guidance and in-app evidence-based treatment support for depression, post-traumatic stress disorder (PTSD), sleep difficulties, and anxiety. BBN contains many of the necessary components to promote self-management of these conditions. We will evaluate the apps feasibility and acceptability among underserved patients (e.g., African Americans and patient with lower socioeconomic status) with trauma histories in an integrated primary care (IPC) setting. There are two specific aims: 1) to develop educational materials for patients and behavioral health providers for BBN in IPC, and 2) to conduct a pilot trial of BBN for patients with trauma histories in an IPC setting. To achieve Aim 1, we will conduct focus groups with behavioral health providers and patients to obtain feedback about BBN and training materials. For Aim 2, a feasibility study with 15 patients will be conducted to identify and address any procedural issues and to refine the protocol before conducting the full-scale study.

### **PURPOSE OF THE STUDY AND BACKGROUND**

**2. Purpose of the Study**

**What are the specific scientific objectives of the research?**

1. Develop educational materials for patients with trauma exposure and behavioral health providers for BBN in IPC emphasizing needs of two health disparity populations: African American and low-income patients.
2. Conduct a pilot trial of BBN for patients with trauma exposure in an IPC setting.

**3. Background and Rationale**

**Describe the background of the study. Include a critical evaluation of existing knowledge, and specifically identify the information gaps that the project is intended to fill.**

A majority of US residents (56.7%) with mental health needs do not receive care. Racial/ethnic minority groups face significant gaps in care, with African Americans receiving care at 60% the rate of Whites. Within this context, primary care has become the de-facto mental health system, treating the largest share of those with common mental health conditions. Integrated Primary Care (IPC) models of mental health care appear to reduce these disparities of access but face challenges in treating trauma-related mental health,

especially since the vast majority of patients attend two or fewer sessions. Improving equity in trauma-focused outcomes is a critical public health need, particularly with the persistent disparities in traumatic event exposure and related mental health. Unfortunately, efficacious treatments for trauma-related concerns in IPC require a minimum of eight weekly sessions. Moreover, successful trauma-focused IPC interventions build on treatments that also face challenges in maintaining fidelity in traditional psychotherapy settings that often treat even less clinical diversity than IPC. We hypothesize that trauma-focused clinician guides that can function in primary care, while also supporting patients who may be unable to attend the suggested several sessions, may hold substantial promise for improving outcomes and equity among racial/ethnic minority and/or low-income populations. Mobile health tools are well-positioned to serve as both clinician guides and patient self-management tools. Mobile in-session guides appear effective in increasing fidelity to trauma-focused care, and similar self-management apps significantly reduce depression and post-traumatic stress disorder, even without clinician guidance. The proposed project addresses critical knowledge gaps: 1) Lack of training materials for patients and providers to implement a mobile app intervention to treat trauma related disorders in integrated care settings; and 2) Lack of clinical protocol to use the mobile app intervention to treat trauma related disorders in integrated care settings.

## **CHARACTERISTICS OF THE SUBJECT POPULATION**

### **4. Accrual**

**A. Is this study conducted solely at sites under the oversight of the UNMC IRB (e.g. UNMC, Nebraska Medicine, CHMC, UNO)?**

Yes

**1. How many subjects will need to be consented (per group, as applicable) in order to achieve the scientific objectives of the research?**

Aim 1: Total 14 - 10 patients and 4 behavioral health providers

Aim 2: Total 45 - Patients (15), BHPs (10), Clinical staff, providers and administration (20)

**2. What is the statistical or other justification for the total number of subjects described above?**

Because of the pilot nature of the study, it is not anticipated that quantitative results will achieve statistical significance. The data will primarily serve to demonstrate feasibility of our approach and success recruitment for a larger clinical trial. We aim for the number indicated in Section II 4 A 1, based on our ability to recruit patients at the clinic during the pilot funding period.

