The second way participants may volunteer for the study is through promotional materials placed within the clinic and via clinicaltrials.gov registry or UNMC research database. These approaches help ensure inclusive opportunities for interested participants who may have or may have previously had experienced trauma-related mental health concerns who are not actively receiving care from a BHP, as their perspectives on the use of the app would still help inform any future adaptations. The in-clinic promotional materials will contain basic information about the study (i.e., that they can help us improve mental health apps), contain the QR code that links to the Redcap information and screening page (which asks their age and if they are receiving care from the approved Fontenelle or Midtown locations), and contact information for the study team where they can reach out for any additional questions.

If the interested participant reaches out to a member of the research team through the clinical trials registry or UNMC research database via email as opposed to scanning a QR code the participant will be emailed the Redcap link which will contain the above described content in addition to resource materials.. The QR code and link for the participants recruited via flyers and trials registry will differ from the ones that BHPs will use to recruit. . This is done because these participants may not have an existing relationship with a BHP and may not currently be engaged in BH services. We therefore will present different information at the end of the screening and consent process to inform them that they may request BH services from their clinic and we will provide a list of BH resources that they may access if they would like to seek services for mental health. For all of the above recruitment methods, using the QR code and screening/consent/download link in this manner, helps reduce barriers to participation and simplifies the process of completing measures and accessing the application.

Educational materials for patients and Behavioral Health Providers (BHPs) for BBN in IPC will be developed.

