**1.) Baseline**

Prior to engagement with the BBN application and as part of standard care at the clinic, a primary care provider at one of the specified Fontenelle, Downtown, Midtown or Bluestem Clinic locations will do a standard "warm handoff" referral to a behavioral health provider (BHP) if the patient is determined to have a behavioral health issue. All participants under Aim 2 will have gone through this process and have discussed identified mental health needs with both the BHP and their primary care provider. They will therefore already be receiving behavioral health services. In this context, BHPs will advertise BBN and the study to participants they believe may benefit, which mimics naturalistic app recommendations in this setting. For such patients, the BHP will provide the patient with a QR code that directs participants to where they can download BBN, which is publicly available. Continuing further with standard care when using apps, BHPs will have discretion as to whom they will recommend BBN. All BHPs have been trained in its use and have viewed its functionality. They will then guide patients through the sections that they perceive as relevant for that patient. Any patient may be directed through these procedures regardless of whether they elect to participate in the research phase. Thus, all Aim 2 procedures to this point are for standard of care. However, they must have had BBN recommended to them by the BHP in order to be eligible for Aim 2 research. For any adult participants (i.e., 19+ years of age) to whom they introduce BBN, BHPs will be asked to advertise a research study on the use, perceptions and initial effectiveness of BBN. To do so, they will use flyers with a QR code that links to a Redcap survey. The BHP will inform the patient that participation in the

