study is voluntary and does not affect their care or access to BBN. The BHP will also assist the patient with the QR code, if necessary, but it is anticipated that participants will interact with this link after the session has ended, which will reduce both patient and provider burden by minimizing disruption to services. The BHP will be trained to problem solve QR code usage with the patient to ensure they can access the link before leaving. The Redcap survey will begin with a modified consent form (it is modified in accordance with the prior waiver of written consent we received previously where participant will confirm the consent electronically). If participants agree to participate in the study, they will then complete a series of questionnaires. All questionnaires are standard in survey research and do not contain any items that identify risk or result in significant distress. They are listed under Research Assessment below. The measures do contain an assessment of stressful event exposure, but prior studies indicate that such measures do not significantly increase participant distress and more frequently report research studies involving such measure as a positive experience overall (Jaffe et al., 2015). Further, the consent procedures will explicitly suggest that participants complete the survey in a private setting and inform the participants that the study will contain questions about stressful life experiences. Additionally, participants will be afforded the opportunity to complete the study in a private setting at the clinic, though we anticipate some participants may choose to complete the survey after. They will be advised that they should complete the consent form and survey within two days of their appointment. At the end of the survey, they will be given information that they should reach out to their BHP if they would like to further discuss any symptoms or topics discussed during the assessment and that they may contact the research team with any questions about the study. The Redcap will also automatically redirect to a separate survey where participants can provide contact information for compensation and follow-up phone surveys (see Follow-up Phone surveys below). Participants will be able to provide contact information for compensation and still decline participation in follow-up phone surveys. Participants will also be able to indicate a preference for completing follow-up surveys electronically and receiving the link via email or text or completing the survey over the phone. They will be asked to provide the contact information corresponding with their preference.

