
The patient will continue to meet with their BHP as determined by the standard of care interactions. And, if deemed appropriate the BHP will highlight features contained in BBN for patient to use in between appointments.

2.) Recruitment for the study will occur in the manner described above in addition to this advertising opportunity to participate using Opt-in registry email which is described below. The opt in registry will be used to identify patients who meet the inclusion criteria and who have had an appointment with the BHP at one of the participating sites within the last three to six months. The Opt in email will provide basic information about the study and include a link which will take the interested participants to the same redcap survey described above which contains the informed consent, contact information for research team members for any questions prior to selecting to proceed, followed by research related questionnaires.

Participants choosing to participate with the Opt-in format will have already an established relationship with the BHP, documented trauma condition within the electronic health record and expressed interest in participating by proceeding from the opt-in initial inquiry. Upon completion of the initial baseline data collection from the participants, BHPs will made aware of the patients expressed interest through the opt-in recruitment process in order to incorporate the app use into subsequent standard of care appointments with the patient. This process will mimic the in-person appointments.

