**D. Identify:**

**1. All procedures, interventions, evaluations and tests performed solely for research purposes (eg, administration of an investigational drug or a new psychological assessment instrument; randomization)**

BBN is being used for the purposes of research.

The focus groups conducted for Aim 1 are for the purpose of research.

We will ask the patients to complete the following instruments for the purpose of research for Aim 2:

- THQ
- Promis 8a
- Pittsburgh Sleep Quality Index
- PCL-5
- MAUQ
- User Burden Scale

We will ask the BHP to complete Self-Management Support in Behavioral Health Organizational Assessment Tool (SMS) and a 5-item comfort level questionnaire.

**2. All procedures, interventions, evaluations and tests performed for clinical indication but more frequently than they would be if the subject was not participating in the research (eg, extra blood tests; additional radiology exams)**

Not Applied.

**E. Describe briefly the statistical methods used to analyze the data (or reference the appropriate section of the detailed protocol or grant).**

Aim 1:Qualitative data will be analyzed using a directed content analysis approach.

Peer debriefing and member checking will be utilized to validate the data.

Aim 2:Quantitative data regarding usability, acceptability and feasibility will be tabulated and summarized using frequencies and percentages. Qualitative data will be analyzed using a directed content analysis approach. Interviews will be transcribed verbatim and uploaded to QSR NVivo 12. Data will be validated through the process of peer debriefing and thick description. Additionally, for usability, acceptability, and feasibility, both quantitative and qualitative data will be integrated and analyzed collectively. A linear mixed effect model (LMM) will be fitted to analyze each continuous outcome measured at different time points

to estimate the potential intervention effect size for future design of larger clinical trial. Transformation of continuous outcome will be performed as needed to satisfy distribution assumption. A generalized linear mixed effect model (GLMM) with cumulative logistic link will be fitted to analyze ordinal outcome. Analysis will be performed using SAS version 9.4 (SAS Institute, Cary, NC).

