**D. How much time will be allotted to the process of consent?**

The consent process is likely to take between 5-10 minutes. However, more time will be provided if needed. We will follow up with the BHP, Clinical Staff, Providers and Administration's manager to determine BHP, Clinical Staff, Providers and Administration interest and invite those interested in participating to complete the informed consent. BHPs at the participating clinic site will identify patients who meet the eligibility criteria and determine interest in participation.

**E. How will the process of consent be structured for subjects who are likely to be more vulnerable to coercion or undue influence?**

Informed consent will be completed in the office of the BHP or with UNMC research Team member on this IRB approved who is identified via clinical trial registry or during their standard of care appointment. Consent will be completed virtually or in written format for in person visits, as such, it will be read aloud to participants. Participants will have additional time, if needed, for delayed consent and encouraged to discuss their participation with family/friends. Only Citi trained and UNMC IRB approved members of this IRB application will be performing consent.

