**2) Describe how the research could lead to the development of important biomedical knowledge.**

Our results will directly inform how technology-based strategies may improve trauma-focused care for underserved populations and shape procedures for a larger clinical trial that may be conducted with the fully-developed and refined educational materials and procedures based on analyses from these data.

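### Recruitment success is a main use of the Aim 2 pilot data, but no count of patients offered the study and no recruitment-route field is planned, so uptake on the provider route, and hence overall, is unlikely to be recoverable.

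*Combined protocol and SAP*

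**What the plan says.** Item 4.A.1 sets 15 patients for Aim 2. Item 4.A.2 gives no power argument. It bases the number on what the clinic can recruit in the funding period and states the purpose as "The data will primarily serve to demonstrate feasibility of our approach and success recruitment for a larger clinical trial". Addendum B, item 2, says the results will "shape procedures for a larger clinical trial".

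Item 12.B describes two Aim 2 routes, and item 29.A repeats them.

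- **BHP route.** The provider introduces the app and advertises the study with a QR-code flyer: "BHPs will have discretion as to whom they will recommend BBN". On timing, "it is anticipated that participants will interact with this link after the session has ended". Items 29.A and 29.B also allow consent during the visit.
- **Opt-in email.** Patients seen by a BHP in the previous three to six months are sent "a link which will take the interested participants to the same redcap survey described above". After baseline, BHPs are told which patients came this way.

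Item 29.D adds that "BHPs at the participating clinic site will identify patients who meet the eligibility criteria and determine interest in participation". For Aim 1, item 12.B states that the QR code and link for flyer and registry recruits "will differ from the ones that BHPs will use to recruit". No equivalent is stated for Aim 2.

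The analysis text for Aim 2 (item 12.E) says: "Quantitative data regarding usability, acceptability and feasibility will be tabulated and summarized using frequencies and percentages". It names no recruitment measure and no denominator.

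**The concern.** A percentage for recruitment needs a count of people approached, and the plan supplies only the people who enrolled. Reaching 15 within the funding period shows that accrual to that number was possible. It does not show how many patients had to be approached for each enrolment, or whether the provider or the email produced them. Those two facts would help set the number of sites, the staff time and the recruitment period of a larger trial.

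The interviews in item 12.B do not fill the gap. Patient interviews reach only people who enrolled, and interviews with BHPs and staff give opinions on feasibility, not a rate.

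The omission is also hard to repair afterwards on the BHP route, because the missing people are those who never opened the link.

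**Working it through.** **Plan's own figures.** Aim 1: 10 + 4 = 14. Aim 2: 15 + 10 + 20 = 45. Both totals agree with item 4.A.1. The 15 patients rest on recruitment capacity, so there is no sample-size formula to reproduce.

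**Search for a denominator.** Each place that could supply one was read.

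- Item 12.B, Aim 2 baseline and opt-in text: flyers, QR codes and emails are described, but no count of any of them and no route field.
- Item 12.B, use of the app: the app captures utilization only. Downloads cannot stand in for offers, because the app is public (item 14) and may be recommended whether or not the patient joins the research.
- Item 12.B, data storage, and item 15.B: the BHP list links names to study IDs and is not described as a list of patients approached. The log for registry contacts belongs to a route that item 18.A confines to Aim 1.
- Items 12.B (data analysis) and 12.E: no recruitment measure.
- Items 29.A to 29.D: BHPs establish interest, but no tally of the result is planned.

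**What could be reconstructed.** The number of opt-in emails sent could probably be retrieved, and opt-in enrollees are made known to BHPs. REDCap could show people who open the link and decline. Neither reaches the patient who was handed a flyer and did nothing, so the BHP denominator, and with it the overall one, stays unknown.

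**Size.** Uptake = x/n, with x enrolled and n offered. The exact (Clopper-Pearson) 95% limits are the 0.025 quantile of Beta(x, n − x + 1) and the 0.975 quantile of Beta(x + 1, n − x). Approaches per 100 enrolled = 100 × n/x. Only x = 15 comes from the plan; every n, and the split by route, is an assumption.

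| Assumed case | x/n | Uptake | Exact 95% CI | Approaches per 100 enrolled |
|---|---|---|---|---|
| Few offered | 15/20 | 75% | 51 to 91% | 100 × 20/15 = 133 |
| Moderate | 15/40 | 38% | 23 to 54% | 100 × 40/15 = 267 |
| Many offered | 15/150 | 10% | 6 to 16% | 100 × 150/15 = 1,000 |
| Last case, BHP part | 10/20 | 50% | 27 to 73% | 100 × 20/10 = 200 |
| Last case, email part | 5/130 | 4% | 1 to 9% | 100 × 130/5 = 2,600 |

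The last two rows add up to the third (10 + 5 = 15 and 20 + 130 = 150). They show that a pooled 10% could hide two very different routes. The intervals for 75% and 10% do not overlap, so even 15 enrolments could separate a high yield from a low one.

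**The case against.** The best reply is that recruitment success may simply mean reaching 15 in the funding period. Only item 4.A.2 mentions it, and the objectives name no recruitment measure. Where item 12.B spells out feasibility, it means using the app and the clinical protocol in practice. The Addendum B sentence concerns strategies, materials and procedures in general. This is an IRB application form, and none of the questions shown asks for a screening log. Part of item 25.A, on recruitment, is also missing from the text available. These points limit how firmly silence can be read. They do not supply a denominator, and accrual alone is a thin basis for planning a larger trial.

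It is also fair that the counts would be imprecise and selected. In the illustration the BHP-route interval runs from 27 to 73%, and the BHP chooses whom to approach, so the rate would not describe all referred patients. That stands, and the report should say so. The tally also adds work for BHPs, whose burden the protocol tries to keep low.

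Two stronger readings are tempting, and the documents support neither.

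- A reader might infer that uptake cannot be reported on any route. Emails could be counted and opt-in enrollees are identifiable to BHPs, so the loss is confined to the BHP route and the overall figure.
- A reader might infer from the follow-up text in item 12.B that usability and burden ratings would be collected at baseline, before the app is used. That text introduces both instruments only in its 6-week paragraph, and the measurement list places them after a second visit.

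**Conclusion.** The point holds for the missing count and the missing route field. The plan names recruitment success as a main use of the data but does not plan to collect what a recruitment rate needs. Followed as written, it is likely to lose BHP-route and overall uptake for good; email-route uptake is recoverable but not promised.

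With 15 enrolled, the plan is compatible with 75% uptake if 20 were offered and 10% if 150 were, a 7.5-fold difference in approaches per enrolment (1,000/133). Those denominators are illustrations, not estimates. The conclusion also assumes that no count is described in the parts of the form that were unavailable.

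The gap biases no outcome estimate and raises no safety issue. It is an improvement worth making before or during recruitment, because the BHP count is unlikely to be recoverable afterwards.

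**What to change.** 1. **Count offers.** Each BHP keeps a running tally, without identifiers, of patients first offered the study, whether by flyer, QR code or consent in the visit. The team logs opt-in emails sent.
2. **Record route.** REDCap captures route by separate links, as Aim 1 already does, or by one field. Fix in advance how a patient reached both ways is classified, for example by first route. An identifier-free tally cannot remove such overlaps from the overall denominator, so say so in the report.
3. **Settle the registry route.** One list of Aim 2 inclusion criteria in item 9 admits patients who contact the team through the trials registry, while item 18.A restricts that source to Aim 1. Reconcile the two; if the route is kept for Aim 2, count it as well.
4. **Report** uptake overall and by route with exact 95% CIs. State that BHP-route uptake is among patients the BHP chose to approach, and that by-route estimates from 15 patients will be imprecise.

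The cost is a tally sheet, an email log and one REDCap field or second link. The drawbacks are a small burden on BHPs and possible under-counting when an offer is not noted, which would overstate uptake. Patients complete no added assessment, beyond a route question if a field is used.

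Separately, and as wording only, two parts of item 12.B need reconciling. The follow-up text makes the 2-week survey the same as baseline, whereas the measurement list sets the Trauma History Questionnaire at baseline. The second visit that times the mHealth App Usability Questionnaire and the User Burden Scale should be defined.
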